5.3 Efficacy analysis

5.3.1 Hypothesis

The main hypothesis is that FDC (either at single or 3-day regimens) will be more effective against STH than the current strategy (single dose ALB alone).

Specific hypotheses:

- Primary Efficacy Endpoint: Higher estimated CR for *T. trichiura* 21 days after treatment, using microscopy in participants allocated to arms 2 and 3 than to arm 1.
- Secondary Efficacy Endpoint(s):
 - Higher estimated CR for hookworm and *S. stercoralis* 21 days after treatment using microscopy in participants allocated to arms 2 and 3 than to arm 1.
 - Higher estimated ERR for *T. trichiura* 21 days after treatment using microscopy in participants allocated to arms 2 and 3 than to arm 1.
 - Higher estimated CR for hookworm, *T. trichiura* and *S. stercoralis* 21 days after treatment, using qPCR in participants allocated to arms 2 and 3 than to arm 1.

5.4 **Primary efficacy outcomes analysis**

The primary efficacy endpoint for the efficacy phase III trial is the cure rates for *T. trichiura* 21 days after treatment using microscopy. The analysis will be conducted on the ITT population and in the sensitivity population (per protocol). The analysis will include both Phase II and Phase III participants. The Cochran–Mantel–Haenszel (CMH) test, controlling the effect of site if that is appropriate (sufficient participants), will be used to compare the cure rates for the 3 treatment groups. A participant is considered cured if the baseline egg count or larval count is not 0, and the post-treatment egg count or larval count is 0. Similarly, a participant is considered to have treatment failure if the baseline egg or larval count is not 0.

A total of 2 stool samples (1 pre-treatment and 1 post-treatment) will be obtained from each participant. The primary efficacy analysis will be based on ITT population. Efficacy for each type of infection will be analysed separately. A participant with multiple infections will be included in the analysis of each target species that the participant is infected with.

Stool sample collected pre-treatment will be used for the baseline information, and stool sample collected post-treatment will be used for the post-treatment information in the statistical analysis.

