5.4.1 Secondary efficacy outcomes analysis

The analysis will be conducted on the ITT population and in the sensitivity population (per protocol)

The secondary efficacy endpoints for the phase II and phase III are the following:

- CR for *T. trichiura* 21 days after treatment, as determined by microscopy (phase II).
- CR for hookworm and *S. stercoralis* 21 days after treatment, as determined by microscopy (phase II and phase III).
- ERR for *T. trichiura* 21 days after treatment, by microscopy (phase II and phase III).
- ERR for hookworm 21 days after treatment, by microscopy (phase II and phase III).
- CR for *T. trichiura*, hookworm and *S. stercoralis*, by PCR (phase II and phase III).
- Parasite burden decrease after 21 days for *T. trichiura*, hookworm, and *S. stercoralis*, by PCR (phase and phase III).

The first 2 endpoints above regarding the CR will be analyzed using the same approach as the primary endpoint analysis.

Egg reduction rate (ERR) for each species (for *T. trichiura* and hookworms) at end of treatment period will be estimated. *S. stercoralis* will not be evaluated by this analysis.

$$ERR (geometric mean) = 1 - \frac{e^{\frac{1}{n}\sum\log(EPG \ follow \ up+1)} - 1}{e^{\frac{1}{n}\sum\log(EPG \ baseline+1)} - 1}$$

The logarithmic transformation will be conducted. As there may be participants with a count of zero eggs in the post-treatment stool sample, a value of 1 will be added to total egg count at baseline and total egg count at post-treatment so that the logarithmic transformation can be applied. The geometric mean will be used to summarize the mean egg count at pre-treatment and post-treatment visits and in the calculation of the mean percent egg reduction. Treatment differences will be evaluated by an analysis of covariance (ANCOVA), in which the logarithm of the egg count at post-treatment is the dependent variable, site (if appropriate), and treatment as fixed effect, and the logarithm of the egg count at pre-treatment is the covariate. Baseline egg count will also be analysed as an independent variable that conditions treatment response [11].

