Cure rates will be also calculated by qPCR. For this, a participant is considered cured if the mean Ctvalues are less or equal than 40 at baseline, and greater than 40 after treatment. When there are nondetectable levels of DNA in the sample, it will be categorized with a Ct-value equal to 50. Cochran– Mantel–Haenszel (CMH) test, controlling the effect of site if that is appropriate (sufficient participants), will be used to compare the cure rates for the 3 treatment groups. In addition, Kappa test and the Fisher 's exact test or chi - square test will be used to compare the CR obtained by Kato-Kats and PCR for the same treatment arm.

Correlation between Kato-Katz counts and qPCR Ct-values will be explored through Pearson's or Spearman's (according to the underlying distribution) correlation tests. Different regression methods to predict EPGs based on Ct-values will be explored.

Increases in Ct-values after treatment will be considered as a reduction in parasite load. To measure whether the increase in ct is significant in each treatment arm, the "Wilcoxon signed-rank test" will be used.

The qPCR will allow the identification of hookworm species (*N. americanus* and *A. duodenale*), so it will be evaluated if there are differences in the response to treatment for these species. Kappa test will be used for the evaluation of both tests in the calculation of CR.

Relevant covariates will also be included in the data analysis. Particularly, HIV infection will be assessed as a covariate in participants recruited in Mozambique.

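### The PCR parasite-burden endpoint has only a before-after test within each arm, so it cannot show whether FDC or FDCx3 lowers parasite load more than albendazole

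*SAP*

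**What the plan says.** SAP 5.4.1 lists among the secondary efficacy endpoints "Parasite burden decrease after 21 days for" *T. trichiura*, hookworm and *S. stercoralis*, by PCR. It sets the measure: "Increases in Ct-values after treatment will be considered as a reduction in parasite load". It then names one test, the Wilcoxon signed-rank test, "To measure whether the increase in ct is significant in each treatment arm". When no DNA is detected, "it will be categorized with a Ct-value equal to 50". A sample counts as PCR-positive at a mean Ct of 40 or less.

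Other endpoints in the same section do get between-arm tests. For PCR cure, a Cochran–Mantel–Haenszel (CMH) test "will be used to compare the cure rates for the 3 treatment groups". For egg counts there is an ANCOVA of log post-treatment count on treatment, site and log baseline count, but *S. stercoralis* is excluded from it.

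Protocol 9.5.3 gives no test for PCR burden. For PCR it covers only correlation with Kato-Katz and kappa agreement on cure.

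SAP 5.3.1 states: "The main hypothesis is that FDC (either at single or 3-day regimens) will be more effective against STH" than albendazole alone. The specific hypotheses listed there and in Protocol 9.1 cover cure by microscopy, egg reduction and cure by PCR, not PCR burden.

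**The concern.** A signed-rank test within one arm asks whether Ct rose in that arm. The trial asks whether it rose more with FDC than with albendazole. Albendazole is an active control, so its Ct may rise too, and three significant before-after tests carry no information about the difference.

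A mixed result is worse, because it invites a comparison of p-values. Significance in an FDC arm but not in the albendazole arm looks like superiority. For *T. trichiura* the albendazole arm has 116 evaluable children against 223 in each FDC arm, so that pattern arises readily from sample size alone.

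The raw change also depends on baseline load. A cleared child's change is 50 minus baseline Ct, and low Ct means heavy infection: baseline 20 gives a rise of 30, baseline 35 a rise of 15. Unadjusted change therefore partly reflects how heavily an arm was infected at entry.

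**Working it through.** **1. The plan's own figures.** No power is stated for PCR burden. For *T. trichiura* cure, albendazole vs FDC, the inputs are 116 and 223 evaluable, 23.7% and 43.7%, two-sided alpha 0.05/3 = 0.0167 (critical value 2.394). The pooled rate is (116×0.237 + 223×0.437)/339 = 0.3686, the pooled SE 0.0552 and the unpooled SE 0.0516. Power = Φ[(0.200 − 2.394×0.0552)/0.0516] = Φ(1.31) = 90.6%, against 91% stated. The other two *T. trichiura* powers reproduce as 100% and 80.2% (stated 100% and 80%). So the arm sizes and rates are read correctly.

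**2. Assumptions for Ct.** The documents give no Ct distribution. Assumed here:
- baseline Ct is normal, mean 30, SD 4, capped at 40;
- cleared children go to 50;
- uncleared children show no systematic change, with noise SD 2 or 4 cycles;
- clearance is the same in all arms, so there is no treatment difference;
- each test is two-sided at 0.05, since SAP 5.4.4 applies no multiplicity adjustment.

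The plan's cure rates are for microscopy; using them as PCR clearance rates is a further assumption.

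**3. Hand check.** A cleared child with baseline Ct of 40 or less rises by at least 10 cycles, almost always more than the noise. With clearance c, the chance that two children's changes sum to more than zero is p = 1 − (1 − c)²/2. Noether's approximation gives signed-rank power Φ[√(3n)·(p − ½) − 1.96].

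At c = 0.237, p − ½ = 0.209. For n = 116: 18.66×0.209 − 1.96 = 1.94, power 97%. For n = 223: 25.87×0.209 − 1.96 = 3.44, power above 99.9%.

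At c = 0.10, p − ½ = 0.095. Power is Φ(−0.19) = 43% for n = 116 and Φ(0.50) = 69% for n = 223. All three significant: 0.43×0.69² = 20%. Albendazole not significant but at least one FDC arm significant: 0.57×(1 − 0.31²) = 52%.

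**4. Results with identical clearance in every arm.** Simulation used at least 500 trials per scenario.

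| Clearance; arm sizes | All three significant: hand / simulated | ALB not, an FDC arm significant: hand / simulated |
|---|---|---|
| 23.7%; 116/223/223 | 97% / about 98% | 3% / 1–2% |
| 15%; 116/223/223 | 66% / 65–70% | 26% / 22–26% |
| 10%; 116/223/223 | 20% / 19–23% | 52% / 49–54% |
| 23.7%; 23/45/45 (phase II) | 19% / 18–20% | 53% / 51–56% |

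For the other species, all three tests are significant in 99 to 100% of trials for *S. stercoralis* (45% clearance, 42/108/107) and in 100% for hookworm (79.5%, 91/91/99). Hookworm is the plan's own case: Protocol 9.2 takes albendazole and single-dose FDC as equal at 79.5%, yet both arms would be significant almost surely.

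**5. A between-arm test on the same data.** With no true difference, a Kruskal–Wallis test of Ct change rejects in about 4 to 7% of trials and a baseline-adjusted ANCOVA of FDC vs albendazole in about 5%. At the planned *T. trichiura* rates, the ANCOVA has about 92 to 97% power for FDC vs albendazole at 0.05, and about 86 to 91% at 0.0167.

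**The case against.** The best defence is that the endpoint was never meant to be comparative. It is absent from the specific hypotheses, and the PCR objective (SAP 2.1.2.2, item 3) concerns how PCR performs against egg counting. On that reading Ct change only describes response in each arm. Superiority is tested elsewhere: the CMH test compares clearance on the same qPCR data, and the ANCOVA compares egg counts.

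Much of this stands. A reader might infer that the trial has no between-arm PCR evidence, or that its superiority claim is at risk. The documents support neither, because PCR cure is compared across arms and the primary analysis does not use Ct. But the SAP lists the endpoint under efficacy and gives it a significance test, not a summary. If description is intended, it should say so. For *S. stercoralis*, Ct change is the only quantitative burden measure, and it has no comparison. The statement that relevant covariates will be included names no model or contrast for Ct, and a signed-rank test takes no covariates.

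The second objection is to the 98%. It depends on 23.7% clearance under albendazole. Protocol 2.1 reports *T. trichiura* efficacy falling from 30% to 15%, and Protocol 2.2 cites a 4% control cure rate in Honduras. With albendazole at 4% and the FDC arms as planned, the albendazole test is significant in only about 11% of trials. This is a fair limit on the figure. It does not rescue the test: at lower clearance the uniform result gives way to the mixed one, which is misleading in the other direction.

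**Conclusion.** The point holds for the quantitative Ct endpoint. As planned, that endpoint cannot show whether either FDC regimen lowers parasite load more than albendazole. This follows from the form of the test and needs no simulation.

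The size of the problem depends on the assumed Ct model, mainly on clearance being a large rise and on no systematic shift in uncleared children. The results barely change between noise SD 2 and 4. The 98% is the upper end of the *T. trichiura* range, with about 20% at 10% clearance. It should not be read as a type I error rate: Ct really does rise in each arm. It is how often all three tests succeed when the arms do not differ. The albendazole-versus-FDC asymmetry, in about half of trials at 10% clearance or at phase II sizes with 23.7%, comes from unequal arm sizes alone.

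This is a secondary endpoint. The primary conclusion and the listed specific hypotheses are unaffected. The change is worth making because it is cheap and because *S. stercoralis* has no other quantitative comparison.

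**What to change.** In SAP 5.4.1, replace the within-arm test as the analysis of this endpoint:

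- For each species, compare FDC vs albendazole and FDCx3 vs albendazole on post-treatment Ct, adjusted for baseline Ct and for site as in the egg-count model.
- Include children with baseline Ct of 40 or less for that species, so that a fall in load is possible.
- Use a rank-based or censored-data ANCOVA, because coding non-detects at 50 leaves a large block of ties that suits ordinary ANCOVA poorly.
- Report estimates with confidence intervals for both contrasts.
- Keep the signed-rank tests as description, and state that significance in one arm but not another is not evidence of a treatment difference.

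The cost is a few lines of SAP text and one extra model per species on data already collected.

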5.4.2 Exploratory efficacy outcome analysis

The exploratory efficacy endpoints for the phase III are the following:

- CR and ERR for *A. lumbricoides* in co-infected participants.
- Prevalence of scabies before and after treatment administration of ALB, FDC and FDCx3.

The summary statistics will be presented for the above exploratory endpoints.

5.4.3 Sub-group analyses

Subgroup analyses will be performed for the primary efficacy outcome on the ITT population. The variables for the subgroup analysis will include:

- Ivermectin drug exposure: categorized by >400 μg/Kg vs ≤400 μg/Kg
- Age: categorized by school-age children (5 to 14 years-old) & young adults (15 to 18 years-old).
- Co-infection: categorized by mono-infected vs co-infected
- Infected with HIV vs no infected with HIV
- Worm burden: categorized by WHO categories of egg burden categories measured by Eggs Per Gram (EPG) through Kato-Katz method [14]:

Species	Light	Moderate	Heavy	
T. trichiura	1 – 999	1000 – 9999	≥10000	
Hookworms	1 – 1999	2000 – 3999	≥4000	
A. lumbricoides	1 - 4999	5000 - 49999	≥50000	

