**ALIVE Study** 

# STUDY POPULATION

#### 5.1 INCLUSION CRITERIA

In order to be eligible to participate in this study, an individual must meet all of the following criteria:

Specific Phase II/Phase III

- 1. Phase II: Positive infection test by microscopy for *T. trichiura*
- 2. Phase III: Positive infection test by microscopy for at least one of the following STH: *T. trichiura* hookworms, and/or larvae of *S. stercoralis*.

To be applied to Phase II and Phase III:

- 1. Weight ≥15 Kg (for phase II and III) and ≤ 45kg (only phase II).
- 2. Male or female, aged 5 to 18 years.
- Female participants who are ≥12 years old (or female who is post-menarche) must have a negative
  urine pregnancy test at screening or at the time of randomisation.
- 4. Ability to take oral medication, willingness to comply with all study procedures.
- 5. Parental acceptance to participate in the study by obtaining a signed and dated informed consent form approved by the Regulatory authorities. Written assent will also be obtained from children aged 12–17 years.

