### 9.5.7 SUB-GROUP ANALYSES

Subgroup analyses will be performed for the primary outcome on the ITT population. The variables for for the subgroup analysis will include:

Drug exposure: categorized by >400 μg/Kg vs ≤400 μg/Kg

Age: categorized by SAC (5 to 14 years-old) & young adults (15 to 18 years-old).

Co-infection: categorized by mono-infected vs co-infected

Worm burden: categorized by WHO categories of egg burden categories measured by Eggs Per Gram (EPG) through Kato-Katz method (1):

Species	Light	Moderate	Heavy
T. trichiura	1 – 999	1000 – 9999	≥10000
Hookworms	1 – 1999	2000 – 3999	≥4000

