3. STUDY DESIGN

3.1 Design

Adaptive phase II/III trial to compare safety and efficacy of the active control arm (current standard of care) against 2 experimental arms.

Phase II component

Uni-centric, 3-arm, parallel, open-label, randomised, phase II trial to determine the safety and tolerability of FDC in paediatric population in different weight strata. Stratification by weight thus recruiting sequentially for safety and tolerability.

- Group 1 (38 participants): with body weight of [23-<30) Kg will receive 300-391 μ g/Kg (FDC 400mg-9mg) or ALB.
- Group 2 (38 participants): with body weight of [30-45] Kg will receive 400-600 μg/Kg (FDC 400mg-18mg) or ALB.
- Group 3 (50 participants): with body weight of [15-23) Kg will receive 391-600 $\mu g/Kg$ (FDC 400mg-9mg) or ALB.

ISGIODAI Barcelona Institute for Global Health

[figure not shown]

Figure 2. Phase II design (Kenya)

Phase III component

A Single-Blinded, Randomized, Multi-Centre, Parallel-Group, Active-Controlled, Superiority Study to Evaluate the Efficacy and Safety of a Single Day or 3-day Single Dose of FDC for the treatment of *Trichuris trichiura*, hookworm, *Strongyloides stercoralis* in paediatric and young adult population.

- a. Arm 1: Single dose of a tablet of ALB 400 mg (active control arm)
- b. Arm 2: Single dose of a tablet of FDC 400mg-18mg (≥45 kg of body weight at baseline) or 400mg-9mg (<45 kg of body weight at baseline).
- c. Arm 3: Daily dose of a tablet of FDC 400mg-18mg (≥45 kg of body weight at baseline) or 400mg-9mg for 3 days (<45 kg of body weight at baseline).

[figure not shown]

Figure 3. phase III design (Kenya, Ethiopia, Mozambique)

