3.3 Treatment

Phase II component

Participants will be randomly allocated with unequal probability to receive either:

Treatment Arm 1: Single dose of a tablet of ALB

Treatment Arm 2: Single dose of a tablet of FDC

Treatment Arm 3: Daily dose of a tablet of FDC for 3 days.

and will be recruited by μ g/Kg of IVM to be received in a sequential manner starting from Group 1 through to Group 3 as shown below:

- Group 1: receiving 300-391 μg/Kg or ALB 400mg- 38 participants (body weight: 23-<30 Kg) will be recruited in this group. (FDC 400mg-9mg).
- Group 2: receiving 400-600 µg/Kg or ALB 400mg− 38 participants (body weight: 30-45 Kg) will be recruited in this group. (Participants <45 kg: FDC of 400mg ALB-9mg IVM, participants ≥45 kg: FDC of 400mg ALB-18mg IVM).
- Group 3: receiving 391-600 μg/Kg or ALB 400mg- 50 participants (body weight: 15-23 Kg) will be recruited in this group. (FDC 400mg-9mg).

Phase III Component

Participants will be randomly allocated with unequal probability (Arm 1 p=0.2, Arm2 p=0.4, Arm3 p=0.4), according to the specific expected cure rate by specie, to receive either:

Treatment Arm 1: Single dose of a tablet of ALB 400 mg (active control arm).

- Treatment Arm 2: Single dose of a tablet of FDC 400mg-18mg or 400mg-9mg.
 - For participants <45 kg of body weight at baseline: FDC of 400mg ALB-9mg IVM.

◦ For participants ≥45 kg of body weight at baseline: FDC of 400mg ALB-18mg IVM.

Treatment Arm 3: Daily dose of a tablet of FDC 400mg-18mg or 400mg-9mg for 3 days.

- For participants <45 kg of body weight at baseline: FDC of 400mg ALB-9mg IVM.
- For participants ≥45 kg of body weight at baseline: FDC of 400mg ALB-18mg IVM.

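### The ivermectin-exposure subgroup (>400 vs ≤400 µg/kg) depends on the assigned arm, so contrasts with albendazole cannot be estimated above 400 and are weight-confounded at or below it

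*SAP*

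**What the plan says.** SAP 5.4.3 states: "Subgroup analyses will be performed for the primary efficacy outcome on the ITT population". The first variable is "Ivermectin drug exposure: categorized by" >400 vs ≤400 µg/kg. Protocol 9.5.7 has the same cut under "Drug exposure: categorized by".

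SAP 4.1 defines ITT as everyone randomised, so the control arm is included. That arm is given in SAP 3.1 as "Arm 1: Single dose of a tablet of ALB 400 mg (active control arm"), with no ivermectin. In SAP 3.3 the Phase III tablet depends only on weight. The lighter band reads "For participants <45 kg of body weight at baseline: FDC of 400mg ALB-9mg IVM"; heavier children, from 45 kg up, get the tablet with 18 mg of ivermectin.

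Eligibility in protocol 5.1 is "Weight ≥15 Kg (for phase II and III) and ≤ 45kg (only phase II"). On the primary analysis, SAP 5.4 says: "The analysis will include both Phase II and Phase III participants". The primary hypothesis (SAP 5.3.1) sets arms 2 and 3 against arm 1.

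Neither document says which stratum an ALB participant enters, or whether exposure in the three-day arm is per dose or cumulative.

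**The concern.** A subgroup variable for a randomised comparison should be fixed before allocation and defined in the same way in every arm. Age, co-infection and worm burden, in the same list, meet that test. Ivermectin exposure received does not, because it follows from the arm assigned.

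What is at stake is how the result would be read. This is a prespecified subgroup of the primary endpoint, in a trial whose stated innovation (protocol 2.2) is to replace weight-based ivermectin with a fixed dose. A difference between the strata would be taken as evidence on dose–response. As defined, it could equally reflect weight or age, and in one stratum there would be no control group.

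**Working it through.** **Reproducing the plan's figures.** Dose per kg = 1000 × mg ÷ kg. All 31 entries of the weight table in protocol 6.1.2 reproduce to rounding: 9000/22 = 409, 9000/23 = 391, 18000/45 = 400. The planned *T. trichiura* powers also reproduce. With 116/223/223 evaluable, cure rates of 23.7%, 43.7% and 59%, and two-sided alpha 0.05/3 (pooled variance), they are 0.906, >0.999 and 0.802, against the stated 91%, 100% and 80%.

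**Where the 400 cut falls, per dose**

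| Group | Ivermectin | Weights with >400 µg/kg |
|---|---|---|
| ALB, either phase | 0 mg | none |
| Phase III FDC, <45 kg | 9 mg | below 9000/400 = 22.5 kg |
| Phase III FDC, ≥45 kg | 18 mg | none (18000/45 = 400 exactly, lower above 45 kg) |
| Phase II FDC, Groups 1 and 3 | 9 mg | 15 to <22.5 kg |
| Phase II FDC, Group 2, protocol 6.1.2 | 18 mg | 30 to <45 kg |
| Phase II FDC, Group 2, SAP 3.3 | 9 mg if <45 kg | none (9000/30 = 300, falling to about 200) |

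**Controls.** Planned ALB *T. trichiura* participants are 26 in Phase II and 103 in Phase III, 129 in all. On the literal reading 0 of 129 are >400, so neither primary contrast exists in that stratum.

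**The ≤400 stratum.** ALB contributes all weights. In Phase III the FDC arms contribute only children of 22.5 kg or more. The contrast with ALB is therefore no longer between groups formed by randomisation.

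**Phase III, dose against weight.** Within the FDC arms, >400 is identical to 15 to <22.5 kg. Every tablet also carries 400 mg albendazole, so the same cut separates children above and below 400/22.5 = 17.8 mg/kg of albendazole. Ivermectin per kg, albendazole per kg, weight and age all change together across it.

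**Pooled set.** Under the protocol, a child of 30 to <45 kg is >400 in Phase II and ≤400 in Phase III. That breaks the identity with weight, but only through a difference between phases, with Phase II run in Kenya alone. It is not randomised and adds no ALB participant to >400. Group 2 has 38 planned participants, about 8/15/15 by arm at 0.2/0.4/0.4. Roughly 30 FDC children (38 × 0.8 = 30.4) therefore change stratum depending on which Group 2 passage applies.

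**Per dose or cumulative.** Three 9 mg doses are 27 mg, and 27000/45 = 600, so every FDCx3 child below 45 kg is >400 on a cumulative count. Three 18 mg doses are 54 mg, >400 below 54000/400 = 135 kg. Cumulative exposure would largely reproduce the arm label.

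**After the fix.** The documents do not give the share of children below 22.5 kg, so the shares here are assumptions. For simplicity the 22.5 kg split is applied to all evaluable participants, at the planned cure rates and two-sided alpha 0.05:

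| Assumed share <22.5 kg | ALB vs FDC | Power in that stratum |
|---|---|---|
| 10% | 12 vs 22 | 20% |
| 20% | 23 vs 45 | 36% |
| 30% | 35 vs 67 | 51% |
| 50% | 58 vs 112 | 74% |

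**The case against.** The strongest reply is that placing ALB children at 0 µg/kg in the lower stratum is an inference. The SAP is silent, and the sponsor may have intended a dose–response within the FDC arms only. The safety section (SAP 5.5) does look at dose–response by number of FDC doses. On that reading there is no distorted contrast with ALB. This is plausible but not written: the subgroup is specified for the ITT population and the primary outcome, whose hypothesis is against ALB. An FDC-only reading would also leave dose inseparable from weight in Phase III.

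A reader might infer that the subgroup can estimate no treatment effect at all, or that it breaks randomisation throughout. The documents do not support that. FDC and FDCx3 follow the same tablet rule, so each per-dose stratum holds both arms and their comparison stays randomised. It is also a planned comparison, with 80% power overall. Nor does >400 mean the lightest children in the pooled analysis, given Phase II Group 2 under the protocol. And an apparent dose effect need not be a weight effect; the two could not be told apart.

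It is also fair to say that this is one of five subgroup variables in the SAP and that no decision rule or sample size depends on it. That limits the consequence but does not make the contrast with ALB valid.

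**Conclusion.** The point holds for contrasts with ALB. On the literal reading, FDC vs ALB and FDCx3 vs ALB cannot be estimated above 400 µg/kg (0 of 129 planned controls). At or below 400 they compare ALB children of all weights with weight-selected FDC children. In Phase III the cut is exactly 22.5 kg, so it cannot isolate dose from weight or age.

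This rests on three things: exposure counted per dose, ALB counted as 0 µg/kg because no other rule is given, and the Phase III tablet rule as written. The number of children affected is unknown because no weight distribution is given. The analysis is secondary, but as written it is unsound against ALB. It should be corrected before the data are analysed.

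**What to change.** First reconcile the passages on the Phase II Group 2 tablet. SAP 3.3 conflicts with protocol 6.1.2 and SAP 3.1, and with the 400–600 µg/kg range that SAP 3.3 itself gives for that group. They decide who is >400.

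Then amend SAP 5.4.3, and align protocol 9.5.7, as follows:

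- Classify every randomised participant, ALB included, by the per-dose µg/kg that their baseline weight would give under the FDC tablet rule of their phase.
- Apply the 400 cut to individual weight. In Phase III this is <22.5 vs ≥22.5 kg. Do not use the Phase II weight group as the stratum: Group 3 spans 391–600 µg/kg, so a child of 22.5 to <23 kg is ≤400 while the rest of the group is >400, and Group 2 includes 45 kg, which is exactly 400.
- State that exposure is per dose.
- Compare arms within stratum, accounting for phase, and give an arm-by-stratum interaction test.
- Report the result as a weight-defined subgroup that does not isolate dose.

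The cost is a few sentences plus the reconciliation. No new data are needed, since weight is recorded in all arms at screening and Day 0. The downside is limited precision: about 20% to 74% power for ALB vs FDC in the lighter stratum over the assumed shares. The change restores a randomised contrast in both strata but cannot make the subgroup a test of dose.
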